#### Source of material

The research material obtained from the subjects will be the results of MR studies. This information will be used solely for research.

#### Subject recruitment

Subjects will be recruited through advertisements, posters, and/or flyers in clinics and/or newspapers. The research procedure will be fully described and potential volunteers will be offered the opportunity to ask questions and read the protocol and consent form. No individual in a supervisory relationship with an investigator will be a participant (employees of an investigator, students in classes with the investigator, or those pursuing a degree under the investigator's direction). Candidates for participation will be provided with our informed consent form and given sufficient time to read it. A physician or a nurse coordinator will verbally review the major points and ask for questions. Those who wish to participate will give their consent by signing the form.

### **B. Potential risks**

#### B1. Risks of the MR scan:

For subjects that are properly screened for the specific contraindications to MR imaging, it is generally believed at this time that the health risks associated with the short-term exposure to radiowaves and high magnetic fields as required for an MR imaging examination are insignificant.

#### B2. Risks of xenon inhalation:

Xenon is a general anesthetic when breathed continuously for long periods of time (minutes) at concentrations greater than 50% (anesthetic dose ~70%). There is also the theoretical risk that HP 129Xe, if given in sufficiently large volumes in forms that do not include oxygen, could cause or exacerbate hypoxia in a subject. However, a recent clinical trial performed at Duke University, where the same protocol was used to image lung ventilation function, has not caused hypoxia but only mild, transient, xenon-related symptoms, consistent with its known anesthetic properties, such as dizziness, paresthesia, euphoria, and hypoesthesia that have resolved soon after discontinuing gas administration(1).

B3. Purity of laser polarized xenon:

The purity of the laser polarized gases is very high because:

1. The initial source of xenon has a purity of at least 99.99%;
2. Only nitrogen is added to the gas before laser polarization;
3. Only room air and oxygen are added to the gas after laser polarization;
4. All chambers into which the gases are transferred are always pumped to a vacuum before gas is transferred into them; and
5. The rubidium vapor used during the polarization process is removed by allowing the polarized gas to pass through either a Teflon filter or a cold trap.

Before xenon is laser polarized, the polarization chamber and connecting tubes are pumped to a vacuum to ensure there are no contaminants that would interfere with the polarization process. For noble-gas laser polarization, xenon, together with nitrogen, which acts as a buffer gas, are then added to the polarization cell. The xenon gas is supplied from specially obtained gas cylinders with a minimum purity of 99.99%. Already present in the polarization chamber is a thin layer of solid rubidium. During the laser polarization, the polarization chamber is heated in order to create an appropriate vapor pressure of rubidium. The laser then excites the rubidium which then exchanges its energy with the noble gas (xenon) to create the laser polarized noble gas. Once polarized, the noble gas is allowed to expand out of the polarization chamber into a glass storage cell, through a Teflon filter or cold trap that removes any remnant rubidium. Before the storage cell is used, however, it is pumped out to a vacuum to remove any gaseous contaminants that might reduce the lifetime of the polarization. Polarized xenon-129 gas is then transferred into a previously evacuated plastic bag. The subject then breathes the undiluted xenon gas through a disposable one-way valve and a connecting tube to the plastic bag.

**C. Adequacy of protection against risks**

**C1. MR Safety Considerations:**

All potential subjects will be familiarized with the MR scanning procedure and will be excluded if they are bothered by the associated noise and confined spaces, or based on the standard exclusion criteria on our MR screening forms. All MR pulse sequences will conform to standard safety guidelines in terms of radio-frequency (RF) power deposition and rate of change of magnetic field (dB/dt).

**C2. Xenon Inhalation:**

The xenon dosing strategy is designed to minimize the previously described xenon physiological effects from the inhalation. In addition, a licensed medical professional will observe the subject whenever they are breathing xenon, and MR compatible monitoring equipment and supplemental oxygen and other equipment for artificial ventilation will be available. In addition, there will be practice sessions to assess the subject's response to the gas mixture. If there is any significant discomfort by a subject, he/she will be excluded from the project.

**C3. Volunteer Confidentiality:**

All MRI images, as well as all records of research, will contain only a study code number and no subject identifying information. Research records will be kept in password protected computer files and will only be available to investigators. The key between subject name and study number will be kept on a flash drive that is stored in a locked file cabinet.

**D. Potential benefits of the proposed research to subjects and others and importance of the knowledge to be gained**

Subjects will receive no direct benefit from participating in this study. Nonetheless, the risks to the subjects from participating are very low as discussed above. This very low, but non-zero, risk to the study subjects is reasonable considering that success of proposed research will yield high societal benefit. Hyperpolarized-gas MRI has already shown substantial potential for providing medically-relevant information, unmatched by any other modality, about important lung diseases such as COPD and asthma. If successful, the proposed research will open a completely new venue for hyperpolarized xenon-129 MRI which, by virtue of producing well defined maps of human BAT and by measuring its temperature non invasively, can provide insights on the mass and function of this tissue in human population. This study will lay the foundation for future application of this technique for purposes such as (i) improving our

understanding of the physiological relevance of this tissue in human populations and its connection with other metabolic diseases. (ii) monitoring BAT function in response to obesity interventions.

#### **E. Inclusion of Women and Minorities**

In keeping with the NIH policy to provide equal participation opportunities for women and for members of minority and ethnic groups, we will ensure that recruitment announcements are accessible to a diverse range of potential subjects, for instance by posting announcements at women's health sites and in Spanish.

No specific gender or racial or ethnic group will be excluded or favored. Based on the racial and ethnic composition estimates for the University of North Carolina at Chapel Hill area it is anticipated that roughly 10% of the study subjects will be from racial minorities and roughly 6% will be of Hispanic or Latino origin. We are aware of no evidence to suggest that the outcome of our evaluations of these new imaging methods would be affected by the racial or ethnic composition of the study population and thus, while we will take steps to ensure equal participation opportunities as discussed above, there is no scientific basis for targeting the enrollment of a specific group in numbers higher than those represented in our underlying population.

#### **F. Number Justification**

A total of 24 subjects will be enrolled in this study. 12 to complete specific aim 1 and 12 to complete specific aim 2. Twelve is the minimum sample size recommended in absence of prior information on which to base our sample size calculation(2). With 12 subjects per group we should be able to obtain positive results (with a 95% confidence interval) on at least 9 subjects if the true prevalence of BAT is 90%(3) (expected prevalence), and on at least 3 subjects if the true prevalence of BAT is much smaller and close to 50% (estimated by FDG-PET scans(4).

1. B. Driehuys *et al.*, Chronic Obstructive Pulmonary Disease: Safety and Tolerability of Hyperpolarized  $^{129}\text{Xe}$  MR Imaging in Healthy Volunteers and Patients. *Radiology* **262**, 279 (January 1, 2012, 2012).
2. S. A. Julious, Sample size of 12 per group rule of thumb for a pilot study. *Pharmaceutical Statistics* **4**, 287 (2005).
3. W. D. van Marken Lichtenbelt *et al.*, Cold-Activated Brown Adipose Tissue in Healthy Men. *New England Journal of Medicine* **360**, 1500 (2009).

4. M. Saito *et al.*, High Incidence of Metabolically Active Brown Adipose Tissue in Healthy Adult Humans: Effects of Cold Exposure and Adiposity. *Diabetes* **58**, 1526 (July 1, 2009, 2009).

**DETAILED BUDGET FOR INITIAL BUDGET PERIOD  
DIRECT COSTS ONLY**
FROM  
06/01/2014THROUGH  
05/31/2015List PERSONNEL (*Applicant organization only*)

Use Cal, Acad, or Summer to Enter Months Devoted to Project

Enter Dollar Amounts Requested (*omit cents*) for Salary Requested and Fringe Benefits

NAME	ROLE ON PROJECT	Cal. Mnths	Acad. Mnths	Summer Mnths	INST.BASE SALARY	SALARY REQUESTED	FRINGE BENEFITS	TOTAL
	PD/PI							
Research Assistant		4	4		24,025	7,600	1,040	8,640
SUBTOTALS →						7,600	1,040	8,640

CONSULTANT COSTS

EQUIPMENT (*Itemize*)

SUPPLIES ( Itemize by category )	19,968
3T scan time	12,240
Enriched Xenon gas mixture	
Volunteer time	1,440

TRAVEL

INPATIENT CARE COSTS

OUTPATIENT CARE COSTS

ALTERATIONS AND RENOVATIONS (*Itemize by category*)OTHER EXPENSES (*Itemize by category*)

CONSORTIUM/CONTRACTUAL COSTS	DIRECT COSTS	
SUBTOTAL DIRECT COSTS FOR INITIAL BUDGET PERIOD ( Item 7a, Face Page )	\$	42,288
CONSORTIUM/CONTRACTUAL COSTS	FACILITIES AND ADMINISTRATIVE COSTS	
TOTAL DIRECT COSTS FOR INITIAL BUDGET PERIOD	\$	42,288

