same protocol will be followed during stimulation of BAT thermogenesis, which will be achieved by an MR compatible water cooling-blanket ( $\sim 15^{\circ}\text{C}$  circulating water temperature), which will be positioned on the lower abdomen/upper leg part of the subjects. The ability to detect BAT by hyperpolarized xenon gas relies on the enhancement in blood flow to this tissue that occurs during stimulation of thermogenic activity. The magnitude of this enhancement seems to be the same, irrespective of the species and of the modality of stimulation of BAT thermogenesis (NE injection of mild cold exposure). Therefore we expect to detect a similar enhancement in the MR signal from xenon dissolved in human BAT. In addition, the use of enriched xenon versus naturally abundant xenon will compensate for the possible loss in xenon polarization during blood transit time. Pre and post stimulation scans will be compared with Matlab to detect differences of more than 5% in the intensity of the dissolved phase xenon images. Detectable BAT volume will be calculated as the sum of pixels whose intensity rose by more than 5% during cold stimulation multiplied by the pixel volume ( $1 \text{ mm}^3$ ). Data will be analyzed using JMP Pro-9.0.0 software (SAS Institute). All P values presented will be two-tailed, and values less than 0.05 will be considered to indicate statistical significance. According to previous studies done in human brain and considering the increase in blood perfusion that occurs in BAT during cold stimulation as well as the higher solubility of xenon in fatty tissues, we expect to be able to obtain images with a resolution of  $0.3 \times 0.3 \text{ cm}$ , high enough to differentiate BAT from the surrounding tissues.

**Aim 2:** Demonstrate detection of BAT thermogenesis in humans.

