This feasibility study will allow us to estimate the standard deviation for the increase in signal from xenon dissolved in BAT and for the increase in BAT temperature that will then be used to power future trials to investigate the incident of this tissue in the healthy human population and the association between BMI and BAT thermogenic activity. For these aims we plan on enrolling a total of 24 healthy subjects (12 for aim 1 and 12 for aim 2) with a BMI ranging between 18 and 28. Twelve is the minimum sample size recommended in the absence of prior information on which to base our sample size calculation. With 12 subjects per group we should be able to obtain positive results (with a 95% confidence interval) on at least 9 subjects if the true prevalence of BAT is 90% (expected prevalence), and on at least 3 subjects if the true prevalence of BAT is much smaller and close to 50% (estimated by FDG-PET scans).

By the end of the study we expect to have fully assessed the potential of HP xenon to detect BAT mass and activity and to have developed an imaging protocol that can be used in studies aimed to investigate the prevalence of this tissue in humans, its connection with other metabolic diseases such as diabetes, and to study the response to treatments aimed to counteract obesity by increasing BAT mass and or function.

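### The sample-size text counts positive subjects, but neither aim defines a positive subject, and Aim 1's only explicit rule is a 5% pixel rise with no minimum extent or noise limit

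*Combined protocol and SAP*

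**What the plan says.** Section F, Number Justification, and the sample-size paragraph that closes the APPROACH section give the same statement. Enrolment is "12 to complete specific aim 1 and 12 to complete specific aim 2". The number rests on a pilot-study rule of thumb: "Twelve is the minimum sample size recommended in absence of prior information on which to base our sample size calculation". The expected yield follows: "With 12 subjects per group we should be able to obtain positive results (with a 95% confidence interval) on at least 9 subjects". This first count assumes a prevalence of 90%. The lower case is worded "on at least 3 subjects if the true prevalence of BAT is much smaller and close to 50" per cent. The unit is the subject, and the statement covers each group of 12, so both aims.

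Under Aim 1, the scans before and during cooling are compared for intensity differences above 5%, with no unit named. A second sentence does name one: "Detectable BAT volume will be calculated as the sum of pixels whose intensity rose by more than 5% during cold stimulation". The total is then scaled to a volume. No minimum number of pixels, cluster size, noise limit, mask or subject-level call is given.

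Under Aim 2, the fitted resonance frequency of lipid-dissolved xenon is used to look for a temperature change. No size of change is named that would make a subject positive.

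**The concern.** The yield is stated in subjects, while the only explicit detection rule works on pixels. Nothing links the two. An analyst must either invent a subject rule after seeing the images or use the nearest rule available, which is that a subject with detectable volume above zero has detectable BAT.

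That default has a weakness. It takes the most favourable of many pixels in each subject, so noise alone can produce a positive. The stated counts of 9 and 3 treat prevalence as the probability of a positive scan, which assumes no false positives and full sensitivity. If subjects without BAT can also score positive, a report of 11 or 12 positives out of 12 could be read as high prevalence when it partly reflects noise. The study is meant to demonstrate detection and to inform later prevalence studies, so such a count could mislead both.

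**Working it through.** **1. Reproduce the plan's counts.** Inputs from section F: n = 12, prevalence 0.90 and 0.50, 95% confidence. Let X ~ Binomial(12, p) and take the largest r with P(X ≥ r) ≥ 0.95.

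- p = 0.90: P(X ≥ 9) = 0.974 and P(X ≥ 10) = 0.889, so r = 9.
- p = 0.50: P(X ≥ 3) = 0.981 and P(X ≥ 4) = 0.927, so r = 3.

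Both counts reproduce as one-sided 95% lower bounds.

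**2. Is 12 itself too few to tell the two cases apart?** Not if subjects are classified accurately.

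| Count | Probability at 50% | Probability at 90% |
|---|---|---|
| 9 or more of 12 | 0.073 | 0.974 |
| 10 or more of 12 | 0.019 | 0.889 |

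**3. What if any risen pixel made a subject positive?** The documents give neither the image SNR nor the number of pixels examined, so both are assumptions here. Take m independent pixels with signal but no true change, and equal independent noise in the two images. Then approximately:

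- chance that one pixel rises by more than 5%: q = 1 − Φ(0.05 × SNR / √2)
- chance that a subject without BAT has at least one such pixel: f = 1 − (1 − q)^m
- chance that a subject is positive, with full sensitivity assumed: prevalence + (1 − prevalence) × f

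At SNR 50: 0.05 × 50 / 1.414 = 1.768, q = 0.0385, and with m = 100, f = 1 − 0.9615^100 = 0.98. The chance of a positive is 0.5 + 0.5 × 0.98 = 0.99 at 50% prevalence and 0.9 + 0.1 × 0.98 = 0.998 at 90%.

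| SNR (m = 100) | q | f | P(X ≥ 10) at 50% | P(X ≥ 10) at 90% |
|---|---|---|---|---|
| 20 | 0.240 | 1.00 | 1.00 | 1.00 |
| 50 | 0.0385 | 0.98 | 1.00 | 1.00 |
| 75 | 0.0040 | 0.33 | 0.18 | 0.96 |
| 100 | 0.0002 | 0.02 | 0.02 | 0.89 |

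At SNR 50 the expected counts are 12 × 0.99 = 11.9 and 12 × 0.998 = 12.0, so the two cases look alike. At SNR 100 almost nothing is lost.

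**4. How sensitive is this to the number of pixels?** At SNR 50 with m = 20, f = 1 − 0.9615^20 = 0.54, and P(X ≥ 10) is 0.46 at 50% against 0.98 at 90%: blurred, not lost. For scale, at the in-plane resolution expected under Aim 1 (0.3 × 0.3 cm), 100 elements cover 100 × 0.09 = 9 cm², a 3 × 3 cm area of one slice. Correlated pixels lower f.

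**5. Pixels without signal.** The INNOVATION section expects background-free maps, so many pixels may hold only noise. If noise in magnitude images follows a Rayleigh distribution (an assumption), the chance that the second value exceeds the first by more than 5% is 1 / (1 + 1.05²) = 1 / 2.1025 = 0.48. Aim 1 states no mask that would remove such pixels, so almost any subject would show some detectable volume.

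**The case against.** The strongest reply is that the documents never say one risen pixel makes a subject positive. That is correct. The pixel sentence defines a volume, and the subject call is simply undefined. A reader might infer the any-pixel rule because it is the nearest explicit one, but step 3 above is conditional on that inference.

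A reader might also infer that 12 was chosen to distinguish 90% from 50% prevalence, or that 12 cannot do so. Neither is supported. Twelve is attributed to a pilot rule of thumb; the two counts describe what 12 should yield; no test between the prevalences is planned; and prevalence is left to later studies. Under an accurate subject rule, 12 separates the cases well.

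It is also fair that the loss depends on unstated quantities. With m = 100 and q = 0.001, f is only 0.095, and 10 or more positives have probability 0.04 at 50% against 0.91 at 90%. A strict enough pixel limit therefore protects the count.

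For Aim 2, one could point to the protocol's expectation that changes as small as 0.2 °C can be detected. That is a claim about sensitivity. It is not stated as the limit for scoring a subject.

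What remains is the core: the yield is expressed in positive subjects, no rule produces that count, and the one explicit Aim 1 rule contains no protection against noise.

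**Conclusion.** The point holds in this form. The counts of 9 and 3 cannot be scored from the plan, because a positive subject is undefined in both aims. If non-zero detectable volume is used for Aim 1, the false-positive rate in subjects without BAT could be anywhere from about 0.02 (SNR 100) to 0.98 (SNR 50) at 100 independent pixels, and a high count might not distinguish 90% from 50% prevalence. These rates rest on assumed SNR, pixel number, pixel independence and full sensitivity; only the binomial figures in steps 1 and 2 rest on the plan's own inputs. The fault is the missing rule and not the sample size. It should be settled before the scans are read, because a rule chosen afterwards would leave the count open to the choice of rule.

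**What to change.** State one subject-level rule per aim, in the Aim 1 and Aim 2 text and in both sample-size statements, and use only that rule for the count of 12.

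- **Aim 1.** First normalise the two images for overall signal difference, by a method named in advance. The budget text says each litre takes at least 40 minutes to produce, so the two images come from different doses; if all pixels shift one way, fallen pixels are no longer a fair reference. Then restrict the comparison to supraclavicular fat. Call a subject positive only if the largest connected cluster of pixels that rose by more than 5% exceeds, by a pre-set margin, the largest connected cluster that fell by the same amount in the same image pair. Report detectable volume as a separate measure.
- **Aim 2.** Call a subject positive only if the frequency shift exceeds a pre-set limit based on measurement noise.

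The cost is wording and a short addition to the planned Matlab analysis, with no new subjects and, for Aim 1, no new scans. The downside is that subjects with very small depots or shifts may be scored negative.

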### **Other Direct Costs**

#### **-Scan time (\$19,968)**

Imaging and spectroscopy experiments in humans will be performed in the Biomedical Research Imaging Center, in which the cost for 1h of scan time is set at \$416. For each subject, the entire imaging session will last for about 2 hours. Therefore funding for a total of 48 hours of MRI scan time are requested.  $(\$416/\text{hour scan time} \times 3 \text{ hours MRI session} \times 10 \text{ subjects})$

#### **-Subject study compensation (\$1,920)**

Each subject will receive a compensation of \$60 for the entire 2 hours imaging session.

#### **-Enriched Xenon gas mixture (\$12,240)**

During the imaging study session the subject will receive two doses of 1L of HP Xenon, spaced 40 minutes apart (40 minutes is the minimum time required to produce a 1L of hyperpolarized xenon gas). For the spectroscopy study the subject will receive a total of 4 0.5L of hyperpolarized xenon every 20 minutes. Funds are therefore requested for 4800L of 1% enriched Xe (quoted at \$5,100 per 2000L cylinder by Linde specialty gas) that will lead to a total of 48L (2L per subject x 12 subjects) of enriched Xenon.

The cost of the non-enriched xenon gas as well as the cost of the other gases needed for the xenon polarizer will be covered in its entirety by the PI funds.

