**APPROACH: Aim1: Demonstrate BAT mass detection in human subjects.**

Our extensive preliminary studies in rodents have shown that, upon stimulation of BAT thermogenesis, an enhancement of more than 10-fold of the MR signal from xenon dissolved in BAT is observed. This enhancement is such that a background free map of this tissue can be obtained in just few seconds (Fig. 1). In addition, when compared to FDG-PET images of BAT, hyperpolarized xenon gas images were able to clearly show BAT in both lean and obese mice and, in the latter, with superior sensitivity (Fig.1b-d).

[figure not shown]
**Fig. 1** Detection of interscapular BAT by hyperpolarized xenon gas MRI (a-b) and FDG-PET (c-d) in a lean (a-c) and obese (b-d) animal. Hyperpolarized xenon gas is clearly more sensitive to the lipid-rich BAT of obese animals (b) than FDG-PET. In d) glucose uptake by BAT is substantially reduced, making it difficult to differentiate BAT from the surrounding tissue.

The broad aim of this proposal is to validate this completely new approach to detect BAT in humans. To this end we will perform HP  $^{129}\text{Xe}$ -MRI of BAT on a 3T clinical magnet using a dual tuned xenon/1H surface coil recently purchased for human BAT studies. The coil will be accurately located above the suprACLAVICULAR area to increase sensitivity to the xenon signal dissolved in the tissue beneath. Conventional  $^1\text{H}$  MRI, which will provide anatomical reference images, will be followed by HP  $^{129}\text{Xe}$  spectroscopy and imaging scans, similar to those used in our rodent studies. Before the acquisition of the xenon images, the subject will be asked to inhale a 1L bag of 100% hyperpolarized and enriched xenon from a Tedlar bag and to hold his breath for about 15-20s. During this time hyperpolarized xenon gas will diffuse from the lung airspaces to BAT in a perfusion-based manner. At the end of the 10 s from the beginning of gas inhalation we will trigger the acquisition of the MR image, which will last for about 10s. The

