Dynamic spectroscopy data have shown the possibility to track BAT temperature over time by measurement of the chemical shift of lipid-dissolved xenon. We demonstrated for the first time MR thermometry by hyperpolarized xenon gas. This method is based on the temperature dependence of the chemical shift of lipid dissolved xenon, which we measured for the first time *in vivo* to be  $-0.2 \text{ ppm}^{\circ}\text{C}$ , (Fig 2.a), i.e. 20 times larger than that of water protons currently used for MR thermometry in lean tissues. This higher sensitivity of lipid-dissolved xenon to temperature, coupled with the lower gyromagnetic ratio of xenon (which makes xenon less sensitive to possible magnetic field in homogeneities present in fatty tissues), allowed us to detect BAT thermogenic activity in mice (Fig.2.b). To this end we will acquire dynamic spectroscopy data from xenon dissolved in BAT during stimulation of BAT thermogenesis by mild cold exposure. During these scans we will track the resonance frequency of lipid-dissolved xenon to detect changes in BAT temperature during thermogenic activity. Although in humans we expect temperature changes less than  $2^{\circ}\text{C}$ , the high sensitivity of xenon to temperature and the narrow line width can allow us to detect changes as small as  $0.2^{\circ}\text{C}$ .

**Fig.2** a) Linear temperature shift of the lipi-dissolved xenon frequency as acquired *in vivo* in an obese mouse. b. Thermogenic activity as detected by hyperpolarized xenon gas. The graph shows the resonance frequency shift of lipid-dissolved xenon and the corresponding shift in BAT temperature right after injection of NE.

For these studies the subject will inhale 4 doses of 1L each of xenon during mild cold exposure, achieved with a water cooling blanket. After inhalation, the subject will be asked to hold his breath for 15-20 seconds, during which we will trigger the acquisition of xenon spectra. The spectra will then be fitted with homemade Matlab routines to extract lipid-dissolved xenon resonance frequency that will be used to detect any change in BAT temperature.

The change in BAT temperature will then be analyzed as function of BMI to establish whether or not there is an association between BMI and BAT temperature increase (Pearson correlation and Spearman correlation coefficient calculation).

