#### **A. Proposed involvement of human subjects**

All research involving human subjects will be carried out at the University of North Carolina at Chapel Hill. All MRI experiments will take place in the Biomedical Research Imaging Center, where the PI's lab for hyperpolarized  $^{129}\text{Xe}$  gas MRI and the 3T Siemens MRI scanner is located. A medical technician, with knowledge and skills consistent with those provided in the American Heart Association's Advanced Cardiac Life Support training will observe the subjects whenever they are breathing xenon gas. Supplemental oxygen (adjusted to flow at 4 liters/minute), suction source, bag valve mask, ventilation device and an airway support device will be available in the MR scanner room. During scanning, a MRI compatible pulse oximeter will be used to monitor the subject's heart rate and blood oxygenation.

A total of 24 healthy subjects, without any metabolic disease, of ages 18 to 40 will be recruited to participate. All subjects will undergo hyperpolarized xenon-129 MR. Healthy subjects are considered those who have never been diagnosed with metabolic diseases, and have no history of any chronic lung disease such as asthma, COPD, or CF.

Since our aim is devoted to test the efficacy of the new methodology for the detection of BAT, there is no justification to scan children under 18 years old. Pregnant or lactating women will be excluded due to potential health risks. All subjects must be able to undergo an MRI examination (e.g., no MRI incompatible implanted devices or other MR contra-indications).

[name] will be present during all hyperpolarized xenon-129 MR scans.

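### The planned Aim 2 xenon dose is four 1 L inhalations in the Approach but four of 0.5 L in the gas budget, and the 48 L gas request matches only the smaller dose if both aims are supplied

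*Combined protocol and SAP*

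**What the plan says.** The dose for the 12 Aim 2 subjects is stated in two places.

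- Approach, Aim 2: "the subject will inhale 4 doses of 1L each of xenon during mild cold exposure". No interval is given there.
- Other Direct Costs, Enriched Xenon gas mixture: "For the spectroscopy study the subject will receive a total of 4 0.5L of hyperpolarized xenon every 20 minutes". The operator between the 4 and the 0.5 is missing from the text as read.

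For Aim 1 the same gas justification says "During the imaging study session the subject will receive two doses of 1L of HP Xenon, spaced 40 minutes apart", and explains the spacing by production: "40 minutes is the minimum time required to produce a 1L of hyperpolarized xenon gas". The Approach for Aim 1 agrees on volume: "the subject will be asked to inhale a 1L bag of 100% hyperpolarized and enriched xenon from a Tedlar bag".

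The enrolment split, in section F (Number Justification), is "12 to complete specific aim 1 and 12 to complete specific aim 2". The gas request is 4800 L of a 1% mixture, "that will lead to a total of 48L (2L per subject x 12 subjects) of enriched Xenon", priced at 12,240 dollars.

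The general procedure in section A (Hyperpolarized xenon-129 MRI) uses a 1 L inhalation with doses at least 15 minutes apart. Section A also says "All subjects will undergo hyperpolarized xenon-129 MR", so that procedure may be meant for both aims, but it gives no separate spectroscopy dose. The practice inhalation, also in section A, is 1 L of natural-abundance xenon and allows the amount to be reduced for a subject who does not tolerate it.

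**The concern.** Two statements of what each Aim 2 subject will inhale differ by a factor of two: 4 L or 2 L of hyperpolarized xenon. Adding one 1 L practice inhalation gives 5 L or 3 L.

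Three things depend on this figure. Section C2 relies on the xenon dosing strategy to limit physiological effects, and section B2 links a theoretical hypoxia risk to large volumes given without oxygen; for Aim 2 the planned strategy is not a single defined quantity. The gas order follows directly from the dose. So does the session time, because production takes at least 40 minutes per litre.

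**Working it through.** **Inputs.** 12 subjects per aim (section F). Aim 1: 2 doses of 1 L (gas justification). Aim 2: 4 doses of 1 L (Approach, Aim 2) or 4 of 0.5 L (gas justification). Gas price: 5,100 dollars per 2000 L cylinder of 1% mixture. Production: at least 40 minutes per 1 L.

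**The plan's own figures first.**

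- Enriched xenon: 4800 L x 1% = 48 L. This reproduces.
- Cost: 4800 / 2000 x 5,100 = 12,240 dollars. This reproduces.
- Printed bracket: 2 L x 12 subjects = 24 L, not 48 L. With 24 subjects, 2 x 24 = 48 L.

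**Gas needed, both aims, no waste.** Total = 12 x (2 x 1 L) + 12 x (4 x Aim 2 dose).

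| Aim 2 dose | Per Aim 2 subject | Aim 1 | Aim 2 | Total | Mixture at 1% | Cost pro rata (dollars) |
|---|---|---|---|---|---|---|
| 0.5 L | 2 L | 24 L | 24 L | 48 L | 4800 L | 12,240 |
| 1 L | 4 L | 24 L | 48 L | 72 L | 7200 L | 18,360 |

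The difference is 72 - 48 = 24 L, and 24 / 48 = 50%. In cost it is 18,360 - 12,240 = 6,120 dollars.

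**Another route to 48 L.** Aim 2 alone at 1 L is 12 x 4 x 1 = 48 L. That leaves nothing for the 24 L of Aim 1, conflicts with the 2 L per subject in the bracket, and does not fit a paragraph that describes both studies before making the request.

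**Is 0.5 L a misread figure?** Two numbers in the same paragraph support reading it as 4 x 0.5 L. At 40 minutes per 1 L, 0.5 L takes 20 minutes, the stated interval; and 0.5 L reproduces the 48 L. This shows which dose was costed, not which is intended.

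**Timing, as an illustration.** Assume one production line at exactly 40 minutes per 1 L. For doses at 0, 20, 40 and 60 minutes, 60 / 40 = 1.5 L is produced by the fourth dose. The stock needed at the first dose is 4 x 0.5 - 1.5 = 0.5 L for 0.5 L doses, or 4 x 1 - 1.5 = 2.5 L for 1 L doses. The time from first to last dose is then:

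- 0.5 L doses, one ready at the start: 0/20/40/60, a span of 60 minutes.
- 1 L doses, one ready: 0/40/80/120, a span of 120 minutes.
- 1 L doses, two ready: 0/20/40/80, a span of 80 minutes.
- 1 L doses, three or more ready: 0/20/40/60, a span of 60 minutes.

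Section B3 mentions a storage cell but gives neither capacity nor holding time. The scan-time justification gives a session of about 2 hours (48 hours / 24 subjects = 2 hours; 416 x 48 = 19,968 dollars), while its own bracket uses 3 hours. A 120-minute span fills the first figure and leaves 60 minutes of the second.

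**The case against.** The 0.5 L figure appears only in a budget justification. Every procedural section that gives a volume uses 1 L per inhalation: the Approach for both aims, the practice inhalation, and the general MRI procedure, which may apply to all subjects. On that view this is one costing line against uniform procedure text. As a description that is fair. It does not remove the conflict: the budget paragraph states what the subject will receive and is specific to spectroscopy, while the general procedure speaks of imaging. If the procedure text governs, the gas justification is wrong and its total too small for both aims. The allowance to lower the amount for intolerance is case by case and does not explain a planned 0.5 L for everyone.

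Several limits on the consequences do stand. A single 1 L inhalation is already part of the practice session, and monitoring and the 15-minute minimum apply at either volume. The documents set no cumulative limit that 4 L would exceed. No effect on an endpoint or analysis has been shown. The 3 L and 5 L totals assume exactly one practice inhalation, whereas section C2 speaks of sessions in the plural.

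The 72 L figure also assumes that Aim 2 uses enriched gas. The Approach calls the gas enriched for Aim 1 but says only xenon for Aim 2, and non-enriched gas is paid for from other funds. The gas justification does describe the spectroscopy doses before its enriched request, so the assumption is reasonable, but it should be stated. Finally, the 20-minute interval is attached only to the 0.5 L dose; applying it to 1 L shows feasibility and is not a second contradiction.

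**Conclusion.** The concern holds and needs correction before the plan is relied on. The nominal Aim 2 exposure is 2 L or 4 L per subject, and no other section settles it.

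If both aims are supplied from the enriched request without waste, 48 L covers 0.5 L doses exactly and falls 24 L short for 1 L doses. The bracket is wrong under either dose. These results are simple arithmetic on printed figures; the timing results also rest on one production line and the assumed number of doses held ready.

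A separate minor inconsistency sits in the same text: the breath-hold is 15-20 s in the Approach and the practice session but 10-15 s in the Hyperpolarized xenon-129 MRI procedure.

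**What to change.** The sponsor should:

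1. Reconcile the Approach for Aim 2, the Hyperpolarized xenon-129 MRI procedure and the gas justification to one Aim 2 dose volume and interval, stated identically in each. This review does not say which volume is right.
2. Recompute the gas total, gas cost and session time from the reconciled figures, stating whether both aims draw on the enriched supply and whether polarized gas is made dose by dose or held in advance.
3. Correct the bracket so that its product equals the stated total.
4. Reconcile the two breath-hold durations.

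The cost is wording and recalculation. If the reconciled volume is 0.5 L and both aims are supplied, the 48 L and 12,240 dollars stand. If it is 1 L, the gas line rises pro rata by 6,120 dollars to 18,360 (3.6 cylinders instead of 2.4), and the session time must be rechecked. Total direct costs are not restated here, because subject payment is printed as 1,440 dollars in the budget table (60 x 24 = 1,440) and 1,920 dollars in its justification.
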